Ibrutinib will be administered once daily continuously until disease progression, intolerance, or completion of 36 cycles, not exceeding 36 cycles since start of therapy whichever comes first. Patients will be instructed to take 420 mg or 560 mg depending on the treating cohort.

Ibrutinib should be administered at about the same time each day orally with 8 ounces or approximately 240 mL of water. The drug should be swallowed intact and subjects should not attempt to crush dissolve the tablets in water. If a dose is missed, the dose may be taken as soon as possible on the same day with a return to the normal schedule the following day. Extra tablets of ibrutinib should not be taken to make up for the missed dose. If a patient vomits the dose, the dose should not be retaken. On days when patients are receiving copanlisib and ibrutinib, patients should take their dose of ibrutinib in clinic just prior to the copanlisib infusion.

9.2. Definitions of dose limiting toxicity, maximum tolerated dose, and recommended phase II dose

A dose limiting toxicity (DLT) is defined as any of the following adverse events occurring within cycle 1 (28 days). A maximum tolerated dose (MTD) is defined as the highest dose studied for which the incidence of DLT is less than 33%. The recommended phase II dose (RP2D) is the dose with clinical efficacy without major toxicity.

- Any AE resulting in a dose delay of >7 consecutive days within the DLT period based on dose modifications in Table 9-6
- Non hematologic AE:
 - Hemorrhage requiring transfusion or procedural intervention, intracranial hemorrhage, intraocular hemorrhage of any grade
 - Grade 4 arterial hypertension
 - Any Grade ≥ 3 AE EXCEPT noted below
 - Grade ≥ 3 nausea, vomiting, constipation or diarrhea persisting for <48 hours
 - Grade ≥ 3 rash or skin hypersensitivity persisting for <7 days
 - <7 days of Grade ≥ 3 fatigue
 - <7 days of Grade ≥ 3 edema
 - <7 days of post infusion blood glucose >250 mg/dL despite optimal glucose management or <2 days of blood glucose >500 mg/dL despite optimal glucose management

- Grade 3 (or 4) isolated electrolyte abnormalities that resolve, with or without intervention, to Grade \leq 2 in less than 72 hours Hematologic AE
 - Any Grade 4 neutropenia lasting more than 7 consecutive days
 - Febrile neutropenia \geq Grade 3 (ANC $<1000/\text{mm}^3$ with a single temperature of $>38.3^\circ\text{C}$ or a sustained temperature of $\geq 38^\circ\text{C}$ for more than 1 hour

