 - Grade 4 thrombocytopenia lasting more than 7 days or Grade 3 thrombocytopenia with evidence of \geq Grade 2 bleeding
- Any Grade 5 toxicity is considered a DLT.

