13.0 CRITERIA FOR REMOVAL FROM STUDY

Patients may voluntarily withdraw from the study or be removed from the study at the discretion of the investigator at any time. Patients may be withdrawn from the study if any of the following occur:

- Disease progression. However, if progression develops after CR while patient is on ibrutinib alone, patients could restart treatment upon radiographic and pathologic expression of disease.
- Ineligibility (at the pretreatment evaluation) of the patient as defined in the inclusion/ exclusion criteria
- Treatment will be discontinued at the request of the patient, refusal of therapy, non-compliance, or upon the development of an intercurrent significant medical illness.
- Significant protocol violation
- Unacceptable toxicity
 - Grade 4 arterial hypertension
 - Grade 4 dermatologic toxicity
 - Non-infectious pneumonitis
 - Drug induced clinically relevant pancreatitis
 - Grade ≥ 3 hypersensitivity reaction
- Decision by the investigator that termination is in the patient's best medical interest.
- Loss to follow-up

- Development of active HBV or HCV infection, hepatitis, or HIV infection
- Pregnancy or a positive pregnancy test
- Death of the patient

In addition to the general study treatment withdrawal criteria, the following study specific criteria will also require premature study treatment discontinuation:

- Use of prohibited medication
- Start of any other anti-neoplastic therapy

If a study treatment withdrawal occurs, or if the patient fails to return for visits, the investigator must determine the primary reason for a patient's premature withdrawal from study treatment and record this information on the End of Treatment CRF page.

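### Section 9.2 exempts short Grade 4 events from the DLT definition and does not clearly count a permanent stop for toxicity late in cycle 1

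*Combined protocol and SAP*

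**What the plan says.** Section 9.2 makes any non-hematologic event of Grade 3 or higher in cycle 1 (28 days) a DLT, subject to a list of exceptions. Four of these have no upper grade. The skin exception reads "Grade ≥ 3 rash or skin hypersensitivity persisting for <7 days". The exceptions for GI symptoms (under 48 hours), for fatigue and for edema (each under 7 days) likewise start at Grade 3 and set no ceiling.

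The list closes with "Any Grade 5 toxicity is considered a DLT". There is no matching line for Grade 4. The electrolyte exception differs in that it names Grade 4 explicitly.

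The only DLT item tied to dosing is "Any AE resulting in a dose delay of >7 consecutive days within the DLT period". It has no grade floor and no relatedness condition. It refers to Table 9-6, which lists dose levels and contains no delay rules. Permanent discontinuation is not mentioned.

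Section 13, which is not limited to one phase, says "Patients may be withdrawn from the study if any of the following occur" and includes "Grade 4 dermatologic toxicity" under unacceptable toxicity. Section 9.7 lets the investigator remove a patient for any toxicity.

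On evaluability, Section 9.7 excludes and replaces patients with fewer than 2 copanlisib infusions or fewer than 14 ibrutinib days, unless a DLT caused the shortfall. Section 14.1 has its own exposure cut-off (75% of planned doses) for patients who stop for other reasons. It also replaces anyone who withdraws from the trial before the end of cycle 1 for a reason unrelated to a DLT.

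**The concern.** The MTD is the primary output of phase I and sets the phase II dose. The 3+3 rule works only if every event that should limit the dose is counted. Two kinds of event may escape:

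- A Grade 4 GI, skin, fatigue or edema event that resolves inside its time limit. It is exempt from the Grade 3-or-higher item on its face, even where Section 13 regards the same event as reason to take the patient off study.
- A permanent stop for an adverse event that meets no other DLT item, such as a lower-grade event, an exempted event, or a cytopenia below the hematologic thresholds. If the delay item does not reach it, Sections 9.7 and 14.1 give no protection, because both protect only stops caused by a DLT.

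Each such patient is either kept as a non-DLT or replaced. Both lower the counted DLT rate and favor the higher dose. With 3 to 6 patients per cohort, one reclassified patient can change the decision.

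**Working it through.** **Which stops the delay item reaches.** The inputs are the 28-day window, daily ibrutinib, and copanlisib on Days 1, 8 and 15 with no Day 22 infusion (Section 9.1.1).

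- First missed ibrutinib dose on Day 21: Days 21-28 are undosed, which is 8 days. More than 7, so caught.
- First missed dose on Day 22: Days 22-28 are undosed, which is 7 days. Not more than 7, so not clearly caught.
- Copanlisib alone stopped after Day 15: no cycle-1 dose is missed, so not clearly caught.
- Section 9.7 replacement route: at most 13 ibrutinib days leaves at least 28 - 13 = 15 undosed days, and a single infusion leaves copanlisib undosed from Day 8. Both exceed 7 days, so on the natural reading these patients are DLTs and are not replaced.

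A patient stopped on Days 22-28 has at least 21 ibrutinib days and can have had all three infusions. Section 9.7 then keeps the patient as a non-DLT. Section 14.1 may replace the same patient if the stop is also a withdrawal from the trial.

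**The plan's own figure.** With DLT rate r, escalation follows 0/3, or 1/3 and then 0/3:

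P(escalate) = (1-r)^3 + 3r(1-r)^2 × (1-r)^3.

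At r = 0.30 this is 0.343 + 0.151 = 0.494. The formula reproduces all eight entries of Table 14-1: 0.973, 0.906, 0.814, 0.709, 0.600, 0.494, 0.309, 0.172.

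**Effect of uncounted stops.** Let T = 0.30 be the true rate with these stops included. Let q be the share of patients stopped permanently in cycle 1 for toxicity that no other DLT item catches, and e the share that goes uncounted. The documents give no value for q, so 1-2% is an assumption.

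- Patient replaced: r = (T-e)/(1-e).
- Patient kept as a non-DLT: r = T-e.
- Natural reading (only Days 22-28 leak, stops assumed even over the cycle): e = q × 7/28.
- Literal reading (the delay item catches no permanent stop): e = q.

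| Reading | q | e | Replaced: r, P | Kept: r, P |
|---|---|---|---|---|
| Natural | 1% | 0.0025 | 0.2982, 0.498 | 0.2975, 0.499 |
| Natural | 2% | 0.005 | 0.2965, 0.501 | 0.295, 0.505 |
| Literal | 1% | 0.01 | 0.2929, 0.509 | 0.29, 0.515 |
| Literal | 2% | 0.02 | 0.2857, 0.524 | 0.28, 0.536 |

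At q = 5% or 10% with replacement, P is 0.513 or 0.531 (natural) and 0.572 or 0.660 (literal).

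The probability of at most 1 DLT in 6, which confirms a dose as the MTD, is (1-r)^6 + 6r(1-r)^5 = 0.420 at r = 0.30. With replacement and q = 1-2% it is 0.424-0.428 (natural) or 0.436-0.452 (literal).

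The natural-reading rows cover Days 22-28 only. A short Grade 4 event in a patient who continues treatment acts like the kept case, with e equal to its own rate, which the documents also do not give.

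**The case against.** The strongest reply is that the delay item already does most of the work. It applies to any adverse event at any grade. Section 9.7 allows a cycle-1 interruption of at most 7 days followed by resumption. A reading in which an 8-day pause is a DLT but never restarting is not would be strained. This stands. A reader might infer from Section 9.2 that no permanent stop counts and that any such patient can be replaced, but the documents do not support that. What is left is Days 22-28, copanlisib-only stops after Day 15, and short Grade 4 events. Letting the delay run past Day 28 would close the first two, but the item limits itself to the DLT period. Section 9.7 also treats delay and discontinuation as different actions.

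Other replies have some force:

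- Section 13 permits withdrawal and does not require it. Table 9-7 says to discontinue both drugs for Grade 4 skin toxicity, but Section 9.7 ties those steps to expansion patients after cycle 1, so it is only supporting evidence.
- Section 13 also lists non-infectious pneumonitis without a grade. That is a weak example, because Table 9-8 continues treatment at Grade 1 and interrupts it at Grade 2.
- Whether CTCAE defines a Grade 4 for every exempted term cannot be settled from the documents. No section suggests that Grade 4 skin events resolve within 7 days.
- The Section 14.1 replacement limb applies only if a stop is also a withdrawal from the trial.
- There are backstops: the unforeseen-toxicity rule at level 1 (9.3), adjustment to the RP2D (9.4), and the Grade 3-or-higher non-hematologic stopping rule (14.2). The last has no short-duration exemption, but its limits run 1/1, 2/2, 4/4, 5/5 and 6/7, against 2 in 6 for DLTs, and it does not see Grade 1-2 stops.

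**Conclusion.** The point holds in limited form. The four exemptions literally include Grade 4, and Section 9.2 leaves late cycle-1 stops and copanlisib-only stops after Day 15 unresolved. The bias runs toward a higher MTD.

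On the natural reading the shift is about 0.4 to 1 point of escalation probability at q = 1-2%. On the literal reading it reaches about 4 points (0.536 against 0.494). In the maximum of 18 phase I patients, q = 1-2% means 0.18-0.36 expected stops, of which 0.045-0.09 fall on Days 22-28. There is only one escalation step, from level 1 to level 2.

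These figures rest on the assumed q, on even timing of stops over the cycle, and on treating the disputed events as true DLTs, so the bias is measured against the definition proposed here. A reader might infer a large distortion by assuming that 10% or more of patients stop uncounted, but nothing in the documents supports such a rate. This is an inexpensive clarification that is worth making. It does not show that the phase I design fails.

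**What to change.** 1. In Section 9.2, limit the GI, rash/skin hypersensitivity, fatigue and edema exemptions to Grade 3. Leave the electrolyte exemption, which names Grade 4 deliberately, as it is.
2. Extend the existing delay item so that it also covers any adverse event leading to permanent discontinuation of either study drug during cycle 1, with the decision to stop made by Day 28. Add no grade floor or relatedness condition, because either would be narrower than the present item. The Day 28 limit prevents a stop in a later cycle from becoming a DLT after escalation has gone ahead.
3. State in Sections 9.7 and 14.1 that such a patient is counted as a DLT and is not replaced.

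The cost is wording in three sections, with no added patients, visits or tests. The downside is slightly less escalation, because some discretionary low-grade stops will now count. If a further 1% or 2% of patients become DLTs (assumed, and not part of T), r is 0.31 or 0.32 and escalation probability falls from 0.494 to 0.474 or 0.454. That loss of 2 to 4 points is as large as the bias being removed or larger, so the case for the change rests on clarity and patient protection more than on the operating characteristics.

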9.7. Dose Continuation, Modification and Interruption

Subjects will be evaluated for AEs at each visit with the NCI CTCAE v5.0 used as a guide for the grading of severity. Prior to completion of cycle 1 in both dose escalation or dose expansion phase, treatment with either ibrutinib, copanlisib or both may be interrupted for \leq 7 days for any reason and then resumed at the same dose. If patients take less than 2 infusions of copanlisib or less than 14 days of ibrutinib during the intended dose of cycle 1, they will be excluded from the DLT analysis and replaced. However if a patient takes less than 14 days of the intended dose of cycle 1 due to a DLT, they will be included in the DLT analysis and not replaced. After completion of cycle 1, study drugs (either ibrutinib, copanlisib) may be interrupted for \leq 28 days for any reason and then resumed at same or reduced dose. The investigator may remove any patient from study for any toxicity if the investigator believes it is in the best interest of the patient to discontinue study treatment.

Intrapatient dose reduction will not be allowed during cycle 1 unless a DLT has occurred and been counted. This is in order to accurately determine the safe and tolerable dose of copanlisib when used in combination with ibrutinib. Dose reductions may be made to ibrutinib and/or copanlisib during cycles 2 and beyond. If a toxicity can be ascribed to a specific study drug, then that drug may be dose modified while the non-offending drug may be maintained. Whether to dose modify ibrutinib or copanlisib is at the discretion of the treating physician.

If the patient experiences unacceptable toxicity that fails to resolve after a maximum dose delay of 28 consecutive days, then the patient should be discontinued from the study treatments. In cases of treatment delays from reactivation of CMV, treatment delays can be extended for up to 2 months. In exceptional situations, if the patient is clearly benefiting from the study treatment (i.e. stable disease or better) and in the opinion of the investigator no safety concerns are present, the patient may remain on the study treatment. Patients who discontinue from study for a study related adverse event or an abnormal laboratory value must be followed as described in Section 10.

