Each patient is allowed a maximum of two dose reduction of each study drug. Dose reduction of copanlisib or ibrutinib indicates treatment at the next lower dose of copanlisib or ibrutinib based on Table 9-6. If after treatment interruption, resolution of toxicity, and treatment resumption at same dose, the subject presents with the same toxicity at the same severity, then the next treatment re-

initiation must resume at the next lower dose level irrespective of duration. A patient must discontinue therapy if after therapy is resumed at a lower dose, the same toxicity recurs with the same or worse severity. Copanlisib and ibrutinib dose modification guidelines for specific toxicities are outlined in Table 9-7.

Table 9-6. Intrapatient dose reduction*

Drug	Maximum Dose Levels	Reduction Dose Level 1	Reduction Dose Level 2
Copanlisib	60 mg	45 mg	30 mg
Ibrutinib	560 mg daily	420 mg daily	280 mg daily

*Dose reduction starts from the treating dose.

Dose escalation is allowed after the DLT period for ibrutinib to the FDA approved dose levels of 560 mg. However, patients will only be allowed to escalate to this dose once the DLT evaluation period for Dose Level 1 has passed and the dose will not exceed what has been deemed the MTD in other patients. There will be no intrapatient dose escalation of copanlisib. Once a dose reduction for copanlisib of a patient has occurred, the dose level may not be re-escalated during subsequent treatment cycles.

The sections below describe dose reduction steps for patients enrolled in the expansion phase of the study. For patients in the dose expansion phase, the dose must be held per these guidelines and these dose reduction steps can be followed after cycle 1 and per discussion with the PI. Inability to meet treatment criteria will result in holding the dose. If patients have been dose reduced to dose level -1 and continue to meet dose modification criteria to reduce the dose, they will be removed from study treatment.

Table 9-7. Dose modification guidelines

Toxicity Category	Severity (CTCAE 5.0 Grade)	Dose Modifications for ibrutinib	Dose Modifications for copanlisib
HEMATOLOGIC			

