Anemia	Grade ≥ 3 (Hgb <8 g/dL)	Investigator discretion for ibrutinib dosing	
Delay copanlisib infusion until Hgb resolves to \leq grade 3
 
Dose reduction by 1 dose level lower at the investigator's discretion. If more dose reductions are required than allowed per protocol, discontinue copanlisib permanently. The lowest dose level is 30 mg.

May dose modify/hold either ibrutinib, copanlisib or both as clinically indicated			
Neutropenia	Grade 1 (ANC < LLN - $1.5 \times 10^9/L$) Grade 2 (ANC < $1.5 - 1.0 \times 10^9/L$)	Maintain ibrutinib dose	Maintain copanlisib dose
	Grade ≥ 3 (ANC < $1.0 \times 10^9/L$)	
Delay ibrutinib dose until resolves to \leq Grade 1, then: If resolved \leq 7 days, then maintain dose level If resolved $>$ 7 days, then reduce 1 dose level
 
Growth factor support is allowed after cycle 1.
	
Delay copanlisib infusion until ANC resolves to $<$ grade 3
 
Dose reduction by 1 dose level lower at the investigator's discretion. If more dose reductions are required than allowed per protocol, discontinue copanlisib permanently. The lowest dose level is 30 mg.
 
Growth factor support is allowed after cycle 1.

	Febrile neutropenia ($ANC < 1.0 \times 10^9/L$, with a single temperature of $\geq 38.3^\circ C$ or a sustained temperature of $\geq 38^\circ C$ for more than one hour)	
Delay ibrutinib dose until resolves to \leq Grade 1, then reduce 1 dose level
 
Growth factor support is allowed after cycle 1.
	
Delay copanlisib until febrile neutropenia resolves
 
Dose reduction by 1 dose level lower at the investigator's discretion. If more dose reductions are required than allowed per protocol, discontinue copanlisib permanently. The lowest dose level is 30 mg.
 
Growth factor support is allowed after cycle 1.

May dose modify/hold either ibrutinib, copanlisib or both as clinically indicated			
Thrombocytopenia	Grade 1 (PLT < LLN - $75 \times 10^9/L$) Grade 2 (PLT < $75 - 50 \times 10^9/L$)	Maintain ibrutinib dose	Maintain copanlisib dose
	Grade 3 (PLT < $50-25 \times 10^9/L$)	
Delay ibrutinib dose until resolves to \leq Grade 1, then: If resolved \leq 7 days, then maintain dose level If resolved $>$ 7 days, then reduce 1 dose level
	Delay copanlisib infusion until platelet resolves to $>75k$

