	Grade 4 (PLT < 25 x 10 ⁹ /L)	Delay ibrutinib dose until resolves to ≤ Grade 1, then reduce 1 dose level	Dose reduction by 1 dose level lower at the investigator's discretion. If more dose reductions are required than allowed per protocol, discontinue copanlisib permanently. The lowest dose level is 30 mg.
Dose modify/hold ibrutinib because of association with hemorrhagic event. May dose modify/hold copanlisib as clinically indicated			
Bleeding	Grade 1 (mild symptoms; no intervention indicated)	Maintain ibrutinib dose	Maintain copanlisib dose
	Grade 2 bleeding (medical intervention indicated/cauterization)	Omit ibrutinib dose until resolves to ≤ Grade 1, then reduce 1 dose level ibrutinib	Delay copanlisib infusion Dose reduction by 1 dose level lower at the investigator's discretion. If more dose reductions are required than allowed per protocol, discontinue copanlisib permanently. The lowest dose level is 30 mg.
	Grade ≥ 3 hemorrhage or hemorrhage resulting in intraocular bleeding causing loss of vision, transfusion of ≥ 2 units PRBCs, and any intracranial hemorrhage	Discontinue ibrutinib	Discontinue copanlisib
RENAL	May dose modify/hold either ibrutinib, copanlisib or both as clinically indicated		
Creatinine elevation	Grade 1 (Cr < 2 x ULN)	Maintain ibrutinib dose	Maintain copanlisib dose
	Grade 2 (Cr 2-3x ULN)	Delay ibrutinib dose until resolves to ≤ Grade 1, then: If resolved ≤ 7 days, then maintain dose level If resolved > 7 days, then reduce 1 dose level	Maintain copanlisib dose
	Grade ≥ 3 (Cr > 3-6 x ULN)	Discontinue ibrutinib	First occurrence: Delay copanlisib infusion until resolves to ≤ Grade 2, no change to next dose Second and Third occurrence: Delay copanlisib infusion until resolves to ≤ Grade 2, decrease by one dose level Fourth occurrence: Discontinue copanlisib *Any grade 4 occurrence: discontinue copanlisib
PULMONARY	Dose modify/hold copanlisib because of association with pneumonitis. May dose modify/hold ibrutinib as clinically indicated		
Pneumonitis	Grade 1		Dose delay copanlisib while treating infection. Resume at same dose once infection resolves
	Grade 2		Dose delay until resolves to ≤ Grade 1. Decrease by one dose level. Second occurrence: Discontinue therapy If no symptom recovery ≤ Grade 1 within 28 days CT scan with lung windows. Consider pulmonary function testing includes: spirometry, DLCO, and room air O ₂ saturation at rest. Repeat at least every 8 weeks (+/- 1)

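### The thrombocytopenia DLT clause is inverted in one narrow cycle 1 case: brief Grade 4 platelets with medically managed Grade 2 bleeding escapes, while Grade 3 platelets with the same bleeding counts

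*Combined protocol and SAP*

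**What the plan says.** The hematologic DLT list in Section 9.2 has one platelet item with two limbs: "Grade 4 thrombocytopenia lasting more than 7 days or Grade 3 thrombocytopenia with evidence of" Grade 2 or worse bleeding. The DLT window is cycle 1 (28 days).

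Three other items in Section 9.2 could catch the same patient:

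- **Dose delay:** "Any AE resulting in a dose delay of >7 consecutive days within the DLT period based on dose modifications in Table 9-6". Table 9-6 lists dose levels only. The hold and restart rules are in Table 9-7.
- **Bleeding:** "Hemorrhage requiring transfusion or procedural intervention, intracranial hemorrhage, intraocular hemorrhage of any grade".
- **Grade 3 or higher catch-all:** this sits under the non-hematologic events.

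Section 9.7 governs dosing in cycle 1. In both phases, either drug or both may be interrupted for up to "7 days for any reason and then resumed at the same dose". It adds: "Intrapatient dose reduction will not be allowed during cycle 1 unless a DLT has occurred and been counted".

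For Grade 4 platelets, Table 9-7 tells the investigator on ibrutinib: "Delay ibrutinib dose until resolves to ≤ Grade 1, then reduce 1 dose level". For copanlisib the thrombocytopenia rows say: "Delay copanlisib infusion until platelet resolves to" above 75k. The paragraph leading into that table says: "The sections below describe dose reduction steps for patients enrolled in the expansion phase of the study". The platelet criterion in Table 9-1 applies from cycle 2.

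**The concern.** A DLT definition should not become more lenient as toxicity worsens. Here a lower platelet count with the same bleeding can receive the milder classification. A charitable reader would take Grade 3 to mean Grade 3 or worse, but the drafting works against that. Elsewhere the same list uses the at-least sign, or names Grades 3 and 4 together, when worse grades are meant. This very clause uses the at-least sign for the bleeding grade. Classification is left to the individual investigator.

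The 3+3 rules in Sections 9.3 and 14.1 act on single events in cohorts of 3 to 6, so one uncounted event can change a decision, and only towards escalation. The patient is affected too, though to a limited extent. Without a counted DLT no dose reduction is allowed for the rest of cycle 1. Dosing can still be held, the investigator may remove the patient, and reductions are open from cycle 2.

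**Working it through.** **1. Apply the Section 9.2 items literally.** In Table 9-7, Grade 3 platelets are 25–50 × 10⁹/L, Grade 4 is below 25, and Grade 2 bleeding calls for medical intervention or cauterization. Rows 1 to 5 have no dose delay over 7 days. In rows 1, 2, 4 and 6 the bleeding is Grade 2, managed medically, and neither intracranial nor intraocular.

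| | Platelets | Bleeding | DLT as written | DLT if the limb read Grade ≥3 |
|---|---|---|---|---|
| 1 | Grade 3 | Grade 2 | Yes (bleeding limb) | Yes |
| 2 | Grade 4, 5 days | Grade 2 | **No** | **Yes** |
| 3 | Grade 4, 5 days | Grade 2, transfusion or procedure | Yes (hemorrhage item) | Yes |
| 4 | Grade 4, 8 days | Grade 2 | Yes (duration limb) | Yes |
| 5 | Grade 4, 5 days | Grade 3 | Yes (non-hematologic Grade ≥3) | Yes |
| 6 | Grade 4, 5 days, delay of 8 days | Grade 2 | Yes (delay item) | Yes |

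Only row 2 changes. The relatedness condition in Section 9.3 applies to rows 1 and 2 alike, so it does not remove the inversion.

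**2. Check that row 2 can occur.** Suppose platelets are 20 with Grade 2 bleeding on day 8 and both drugs are held. By day 15 platelets are 75 or more, the bleeding has settled and dosing resumes.

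- Delay: 15 − 8 = 7 days, which is not more than 7.
- Exposure: copanlisib on days 1 and 15 is 2 infusions. Ibrutinib on days 1–7 and 15–28 is 7 + 14 = 21 days. Section 9.7 excludes only patients below 2 infusions or 14 days. The exclusion in Section 14.1 is for patients who stopped therapy, and this patient resumed. The patient stays evaluable and is scored as having no DLT.
- Recovery passes through 25–50, where ongoing bleeding would meet the Grade 3 limb. Table 10-1 lists cycle 1 visits only on days 1, 8 and 15, so that passage may go unrecorded unless extra counts are drawn.

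With platelets of 30 on day 8 and the same bleeding, the clause is met at once.

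**3. Reproduce the plan's escalation table.** For a true DLT rate p, escalation needs 0/3, or 1/3 followed by 0/3:

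P(escalate) = (1 − p)³ + 3p(1 − p)² × (1 − p)³ = (1 − p)³ + 3p(1 − p)⁵

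At p = 0.30: 0.3430 + 0.9 × 0.16807 = 0.494. At p = 0.20: 0.5120 + 0.6 × 0.32768 = 0.709. Table 14-1 gives 0.49 and 0.71, and its other six entries also reproduce.

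**4. Size, as illustration only.** The documents give no rate for row 2, so the uncounted share u is assumed. P(escalate) is evaluated at p − u. Expected uncounted events are 18u, using the phase I maximum of 18.

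| u (percentage points) | P(escalate), true rate 30% | P(escalate), true rate 20% | Expected uncounted events in 18 |
|---|---|---|---|
| 0 | 0.494 | 0.709 | 0 |
| 0.1 | 0.496 | 0.711 | 0.02 |
| 0.25 | 0.499 | 0.714 | 0.05 |
| 0.5 | 0.505 | 0.719 | 0.09 |
| 1 | 0.515 | 0.730 | 0.18 |

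That is about 2 points of escalation probability per percentage point uncounted. For confirming a level as the MTD, P(at most 1 DLT in 6) = (1 − p)⁶ + 6p(1 − p)⁵. At a true rate of 30% it moves from 0.420 to 0.431 (u = 0.5) or 0.442 (u = 1). Table 9-2 has one upward step, from level 1 to level 2.

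**The case against.** The strongest reply is that Table 9-7 closes the gap. For Grade 4 platelets, ibrutinib is to restart one level lower, and Grade 2 bleeding also calls for a reduction. Cycle 1 reductions are barred unless a DLT has been counted. Ibrutinib held on day 8 then could not restart in cycle 1, the delay would pass 7 days, and the delay item would record a DLT. Only onset in about the last week of cycle 1 would escape. Some text supports applying Table 9-7 in phase I. Sections 9.7 and 9.8 refer to it without a phase limit. The delay item presupposes hold rules that Table 9-6 does not contain. The table's growth-factor note matches the cycle 1 restriction that Section 9.6.1 places on dose escalation.

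This does not settle the matter. Section 9.7 expressly allows a cycle 1 interruption of up to 7 days for any reason with resumption at the same dose, and names no platelet threshold. It also introduces the reduction steps for expansion patients and places them after cycle 1. On that text the day 8 example is permitted, and the delay item is not an assured backstop in phase I.

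The points about rarity do stand. Platelets must recover from 20 to 75 within 7 days in a bleeding patient without transfusion, and Section 9.8 suggests considering platelet transfusion if bleeding diathesis occurs. Extra counts are likely in such a patient and could record bleeding at 25–50. Many investigators would probably read Grade 3 as at least Grade 3. Later related toxicity is still evaluated under Section 14.1, and Section 9.4 allows the phase II dose to be adjusted on safety review.

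**Conclusion.** The clause is wrong as written, and the point is minor. On the literal text, Grade 4 platelets for 7 days or less with medically managed Grade 2 bleeding is not a DLT, while Grade 3 platelets with that bleeding is. No other item in Section 9.2 or 14.1 extends the bleeding limb to Grade 4. Confidence in the reading of the text is high. The effect on the trial cannot be estimated from the documents, because it depends on the assumed rate of a rare combination. At the assumed 0.1 to 1 percentage point, the escalation probability at a true 30% DLT rate rises by 0.002 to 0.021, with fewer than 0.2 expected events across phase I. The direction is certain: a missed event can only make a level look safer.

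**What to change.** In Section 9.2, keep the Grade 4 duration limb and change the bleeding limb to: *Grade ≥3 thrombocytopenia of any duration with evidence of Grade 2 or worse bleeding*. This adds one symbol and three words and removes the inversion. A few more events may count as DLTs. The phase I maximum of 18 patients and Table 14-1 do not change.
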